10. The study team member will share with the patient that they can take as much time as necessary to understand the consent form. Study team members will then ask questions to the patient to clarify whether they understand the information provided in the consent form.
11. Once informed consent is obtained, an Epic documentation (Research note) and research flag will be placed in the EHR.
12. If the patient is non-English speaking, study participation will not be available, given the need for extensive communication needed during CR, especially hybrid CR.
13. After consent is obtained by the research team member and prior to randomization, baseline data (e.g. demographic information, relevant medical history, blood pressure, heart rate)) will be obtained.
14. Following hospital discharge, consented patients will be followed up with a telephone call during a 4-week run-in period to assess their continued interest in study participation, as well as to verify their insurance approval for in-center CR. Those who qualify will then be randomized at a 1:1 ratio to the intervention plus usual care (intervention group) or usual care alone (control group). Usual care is defined as care according to patient care team's standard practice. Randomization will be based on a dynamic randomization strategy that minimizes the difference in age, sex, and treatment modality (cardiac surgery, cardiac catheter-based procedure, or medical therapy alone).
15. If the order for CR referral is not done automatically, we will encourage the primary team to place the order for CR in the EHR and/or place the CR order on behalf of the primary team following attending physician approval, to ensure 100% CR referral rate for all study participants.
16. We will use a random number generator for generation of random number sequences and adopt open source software for dynamic randomization implementation. We will minimize bias by concealed allocation at time of enrollment.
17. Once randomization arm is determined, a study team member will inform each patient of their allocation.

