1. The Corrie app is available on both iPhone and Android platforms. In discussion with an FDA-consultant, because the functionality of the app is as an organizational and navigational tool for patients, it does not require pre-approval from the FDA before use with patients. It falls within the category of mobile apps for which the FDA is exercising enforcement discretion.
2. The Apple Watch, Fitbit, and Omron blood pressure cuff all have received FDA clearance and are safe for patient use (see supplementary documents).

7. Statistical Analysis

The primary outcome measure of the study is the difference in distance participants walked (i.e. functional capacity) between the intervention and usual care groups, as measured by the 6MWT at final study follow-up at 12 weeks post-randomization. Based on the estimates from a prior RCT ⁴¹ in patients with acute coronary syndrome in a smartphone-based, cardiac rehabilitation program, but also accounting for a significant anticipated proportion of cardiac surgery and TAVR patients in our trial population, we assume a pooled standard deviation of 107 meters for follow-up 6MWT distance. and a minimally clinically important difference of 30 meters in 6MWT distance.⁴²

Date: 10.09.2024

Principal Investigator: [name], MHS

Application Number: IRB00308410

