For the trial to demonstrate noninferiority with 80% power, assuming a pooled standard deviation of 107 meters for the follow-up 6MWT and a true 6MWT difference in favor of the Corrie HCR program of 30 m, 160 patients will be required (80 per group) to exclude a difference of >12.5 m in favor of the usual care group. The noninferiority margin of 12.5 m was chosen to represent about 40% of the minimum important difference of 30 m in 6MWT as identified in previous studies. Accounting for an attrition rate of 20% during follow-up after randomization, a total of 200 (100 per group) participants will be randomized in a 1:1 ratio to the 2 treatment arms. In order to accrue 200 patients for randomization, we expect to recruit up to 300 patients, until target randomization number has been met. We will compare the mean level of 6MWT at 12 weeks post-randomization between the intervention and control groups using a generalized linear regression model. The sample size calculation was performed using the TWOSAMPLEMEANS statement in SAS version 9.4 procedure PROC POWER (SAS Institute Inc., Cary, NC), in which the null value option was specified to represent the noninferiority margin.

If a participant has an adverse event that results in them being discontinued from the study or does not engage with the intervention, that participant will be included in the intention-to-treat analysis, which is the primary form of analysis for our study.

In addition to the primary intention-to-treat analysis, a pre-specified, per-protocol analysis will be conducted 1) inclusive of intervention group participants who remain active in the study and engage with the intervention, and separately 2) among those participants (in both control and intervention arms) who have completed at least two in-person CR sessions, in order to assess the efficacy of the intervention.

In addition, pre-specified subgroup analyses will be performed, stratified by: age, sex, treatment modality (cardiac surgery, catheter-based intervention, or medical therapy), and LDL-C level (threshold LDL-C \geq 55mg/dL).

8. Risks

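### The primary 6MWT model names none of the minimization factors; run that way, the noninferiority test is conservative and gives up precision if they are prognostic

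*Combined protocol and SAP*

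**What the plan says.** Section 4 (Study Procedures, item 14) sets the allocation method: "Randomization will be based on a dynamic randomization strategy that minimizes the difference in age, sex, and treatment modality". Treatment modality has three levels: "cardiac surgery, cardiac catheter-based procedure, or medical therapy alone".

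Section 7 (Statistical Analysis) gives the primary analysis in one sentence: "We will compare the mean level of 6MWT at 12 weeks post-randomization between the intervention and control groups using a generalized linear regression model". It names no covariates and excludes none. The three factors appear in that section only as subgroup strata: "pre-specified subgroup analyses will be performed, stratified by: age, sex, treatment modality".

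The sample size is a two-sample comparison of means using an SD of 107 m for follow-up distance, with no reduction for covariates: "160 patients will be required (80 per group) to exclude a difference of >12.5 m in favor of the usual care group". On the source of the SD, Section 7 says that "accounting for a significant anticipated proportion of cardiac surgery and TAVR patients in our trial population, we assume a pooled standard deviation". No significance level is stated.

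**The concern.** Minimization forces the arms to be alike on the chosen factors. If a factor predicts 6MWT distance, the difference in arm means then varies less from one possible allocation to another than it would under simple randomization. A regression with arm alone cannot see this. It leaves the factor's variance in the residual and reports a standard error as if the arms had not been balanced.

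Noninferiority here turns on whether the lower confidence limit lies above -12.5 m. An interval that is too wide makes that harder to show when it is true. The error is on the safe side for a false claim, but a genuine noninferiority result could be missed for want of an adjustment that needs no new data. Because the text is compatible with both models, it also leaves open which interval decides the trial.

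**Working it through.** **Inputs from Section 7.** SD 107 m; assumed true difference +30 m; margin 12.5 m; 80 evaluable per group; 80% power; 20% attrition. The distance from the assumed truth to the null is 30 + 12.5 = 42.5 m.

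**Not in the documents.** The significance level, and the share of 6MWT variance (R²) that the three factors explain. R² is varied from 0 to 0.3.

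**Reproducing the plan's figure.** The unadjusted standard error is 107 × √(2/80) = 16.92 m, so the noncentrality is 42.5 / 16.92 = 2.51. With a noncentral t on 158 degrees of freedom:
- One-sided 5%: power 80.4%, and 80 per group is the smallest size that reaches 80%. This matches the plan.
- One-sided 2.5%: power 70.4%, and 101 per group would be needed. This does not match.

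One-sided 5% is therefore inferred, and the deciding interval is the two-sided 90% interval. Attrition also reproduces: 160 / (1 - 0.20) = 200.

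**Factors left out, full balance (limiting case).** The model still reports 16.92 m, but the true standard error is 16.92 × √(1 - R²).
- Half-width = 1.655 × 16.92 = 28.0 m at any R².
- Power = Φ((42.5 - 28.0) / (16.92 × √(1 - R²))).
- Size at the margin = Φ(-1.645 / √(1 - R²)).

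**Factors included.** Age as one term, sex as one and modality as two leave 160 - 6 = 154 degrees of freedom. Power is from the noncentral t with standard error 16.92 × √(1 - R²).

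| Assumed R² | Power, omitted | Power, included | Half-width, omitted | Half-width, included | Size, omitted (nominal 5%) |
|---|---|---|---|---|---|
| 0 | 80.4% | 80.4% | 28.0 m | 28.0 m | 5.0% |
| 0.05 | 81.1% | 82.2% | 28.0 m | 27.3 m | 4.6% |
| 0.1 | 81.7% | 83.9% | 28.0 m | 26.6 m | 4.1% |
| 0.2 | 83.1% | 87.5% | 28.0 m | 25.0 m | 3.3% |
| 0.3 | 84.7% | 91.1% | 28.0 m | 23.4 m | 2.5% |

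Omitting the factors does not take power below plan, because the 107 m already contains whatever variance they explain.

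**Imperfect balance.** Minimization was simulated for 200 patients with 160 retained at random. Assumed: three age bands, 30% women, modality split 35/50/15%, equal variance share per factor, 80/20 biased coin; 4,000 replicates each for power and size.

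| Assumed R² | Power, omitted | Power, included | Size, omitted | Size, included | 90% CI coverage, omitted |
|---|---|---|---|---|---|
| 0 | 80.3% | 80.2% | 5.0% | 5.1% | 89.6% |
| 0.1 | 80.8% | 83.4% | 4.3% | 4.8% | 91.5% |
| 0.2 | 80.7% | 86.2% | 4.2% | 4.8% | 92.2% |
| 0.3 | 83.0% | 90.5% | 3.0% | 5.1% | 93.2% |

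Monte Carlo error is about 0.6 points for power and 0.3 for size. A separate simulation with the same kind of set-up gave omitted-model size of 4.2, 3.8 and 3.5% at R² 0.1, 0.2 and 0.3. Dropout weakens the balance a little, so the conservatism is somewhat smaller than in the limiting case, but the direction is the same.

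**If the level were one-sided 2.5%.** With 80 per group and R² 0.1, 0.2 and 0.3, power is 71.4, 72.6 and 74.0% without the factors and 74.9, 79.7 and 84.7% with them.

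**The case against.** The strongest reply is that no error has been shown. A regression model may contain covariates, Section 7 does not rule them out, and a bare comparison of two means would hardly need one. This stands to the extent that the consequence follows only if the factors are in fact left out. It does not remove the need to say which model is meant.

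Second, the size is assumed. That is true: R² is not given, and at 0.05 the gain is about one point of power and 0.7 m of half-width. The direction does not depend on the value as long as the factors are prognostic at all.

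Third, the evidence in the documents that they are prognostic is thin. The SD sentence puts cardiac surgery and TAVR together, whereas the minimization factor separates surgery from catheter-based procedures, where TAVR would naturally fall. The sentence shows that the plan regards procedure mix as relevant to the spread of 6MWT. It does not quantify this, and it says nothing about age or sex. This limit is accepted.

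Fourth, no stated goal is harmed: type I error is protected, and the unadjusted test agrees with the unadjusted sample size. That is right, and it is why this is a recommended improvement and not a failure of validity. The assurance on power, however, rests on the inferred one-sided 5%. At one-sided 2.5%, 80 per group gives 70.4% power even when R² is zero. That shortfall would come from the unstated level, a separate matter from the covariates.

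**Conclusion.** The concern holds. The primary comparison is stated without the factors used to allocate patients. If it is run that way and they are prognostic, the interval judged against -12.5 m is wider than the allocation method warrants, and the test is conservative. At an assumed R² of 0.2, the full-balance loss is about 4 points of power (83.1 against 87.5%) and 3 m of half-width (28.0 against 25.0 m). Over R² 0.1 to 0.3 the loss is about 2 to 6 points and 1.4 to 4.6 m. At R² of zero there is no loss.

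These figures rest on the assumed R², the inferred one-sided 5% level and, in the simulations, assumed factor frequencies and random attrition. The error favors caution and the planned power is met at the inferred level, so the matter is one of efficiency and of fixing the primary model in advance. It should be corrected, but it does not threaten the trial's validity.

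**What to change.** In Section 7, state that the primary model is a linear regression of 12-week 6MWT distance on arm, age (as a continuous variable), sex and treatment modality (three levels). State that noninferiority is read from the confidence interval for the adjusted arm difference, and that the unadjusted comparison is a sensitivity analysis.

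The cost is one sentence. The minimization already requires all three factors for every randomized patient, so no new data are needed, and the sample size can stay as it is. The change should be made before anyone sees outcome data by arm.

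### Intention-to-treat inclusion is promised, but the plan gives no way for the expected 20% without a 12-week walk to enter the noninferiority test

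*Combined protocol and SAP*

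**What the plan says.** All references are to the combined protocol and SAP.

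- **Analysis population (section 7).** For a participant discontinued from the study because of an adverse event, or not engaging with the intervention, the plan says "that participant will be included in the intention-to-treat analysis, which is the primary form of analysis for our study".
- **Model (section 7).** "We will compare the mean level of 6MWT at 12 weeks post-randomization between the intervention and control groups using a generalized linear regression model". No covariates, repeated measures, imputation or rule for a missing outcome are named.
- **Size (section 7).** The target is 80% power, with an SD of 107 m at follow-up and an assumed true advantage of 30 m for the intervention. The result is given as "160 patients will be required (80 per group) to exclude a difference of >12.5 m in favor of the usual care group". Dropout is then added on top: "Accounting for an attrition rate of 20% during follow-up after randomization, a total of 200 (100 per group) participants will be randomized".
- **Margin (section 7).** The reason given for its size is this: "The noninferiority margin of 12.5 m was chosen to represent about 40% of the minimum important difference of 30 m".
- **Loss to follow-up (section 4, under treatment failure and participant removal).** Both arms have a trigger for not answering calls after unanswered surveys. The intervention arm has a second one: more than 30 days without using the app.
- **Measurement (section 4, item 29 and Table 3).** The primary walk is taken at an in-person final visit, normally at one site. Table 3 lists the 6MWT only at follow-up. Item 29 mentions a pre-discharge walk, for hospital-enrolled patients only.

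The two per-protocol analyses in section 7 restrict the sample further, so they do not address missing walks.

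**The concern.** A regression on one outcome value has nothing to use for a person without that value, and standard software leaves that person out. The plan promises that discontinued participants are in the primary analysis, but its stated method cannot include those who have no 12-week walk. Someone has to add a rule, and if that happens after the data are seen, the primary result depends on a late choice.

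This matters more than usual for two reasons. The test is for noninferiority with a 12.5 m margin, so if intervention participants who would have walked poorly are the ones missing, the comparison moves toward the conclusion the trial seeks. And the app-use trigger applies to one arm only, so participants could come to be missing at different rates and for different reasons in the two arms. That trigger also conflicts with section 7: a non-engager is to be analyzed there, yet section 4 labels the same person lost to follow-up.

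**Working it through.** **1. Reproduce the plan's size.** Inputs from section 7: SD 107 m, true difference +30 m, margin 12.5 m, power 80%. The distance from the margin is 30 + 12.5 = 42.5 m. Alpha is not stated.

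n per arm = 2 × (z₁₋α + z₀.₈₀)² × SD² / 42.5²

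- One-sided 0.05: 2 × (1.645 + 0.842)² × 107² / 42.5² = 78.4, so 79 by the normal formula and 80 by noncentral t (power 80.4%). This matches 160.
- One-sided 0.025: 100 by the normal formula, 101 by noncentral t. This does not match; 80 per arm would give about 70% power.

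One-sided 0.05 is therefore an inference. Results below are given at both levels.

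Attrition: 160 / 0.80 = 200. The stated power rests on 160 observed walks, leaving up to 200 − 160 = 40 participants, about 20 per arm, without a primary outcome.

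**2. Precision with 80 walks per arm.** SE = 107 × √(2/80) = 16.9 m. To exclude −12.5 m, the observed difference must exceed about +15.5 m at one-sided 0.05, or about +20.9 m at 0.025.

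**3. Bias of an observed-only comparison.** Let m be the fraction missing in an arm, and D the shortfall of its missing participants relative to its observed ones. The mean over all randomized in that arm is the observed mean minus m × D, so

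bias in favor of the intervention = m_I × D_I − m_C × D_C.

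The 20% comes from the plan. D is an assumption, because the documents give no figure, so a range is shown.

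**4. False noninferiority rate.** With the true all-randomized difference at −12.5 m, the rate is 1 − Φ(z₁₋α − bias/SE). For D = 50 at one-sided 0.05: 1.645 − 10/16.9 = 1.05, giving 14.6%.

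| Missing I / C | D in I / C (m) | Bias (m) | Nominal 5% becomes | Nominal 2.5% becomes |
|---|---|---|---|---|
| 20% / 20% | 30 / 0 | 6 | about 10% | about 5% |
| 20% / 20% | 50 / 0 | 10 | about 15% | about 9% |
| 20% / 20% | 100 / 0 | 20 | about 32% | about 22% |
| 20% / 20% | 50 / 50 | 0 | 5% | 2.5% |
| 30% / 10% | 50 / 50 | 10 | about 15% | about 9% |

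Reversing the last row (10% / 30%) gives 0.1 × 50 − 0.3 × 50 = −10 m, a bias against the intervention.

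**5. How large D must be.** A bias equal to the whole margin needs D = 12.5 / 0.2 = 62.5 m when only intervention-arm missing participants differ. If the observed difference were the planned +30 m, losing noninferiority at one-sided 0.05 would need 0.2 × D above 30 − 15.5 = 14.5 m, so D above about 73 m. At 0.025 it would need 30 − 20.9 = 9.1 m, so D above about 45 m. Both hold the SE fixed.

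**The case against.** The strongest reply is that the plan is silent, not wrong. A reader might infer that it specifies a complete-case analysis. It does not: no section limits the model to observed walks, and imputation followed by the same regression would fit the text. Complete-case is only what happens if nothing is added. A reader might also take the step from 160 to 200 as confirming that only 160 will be analyzed. That does not follow, since inflating for attrition is routine under any missing-data method.

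Nor do the documents say that discontinued participants usually have no walk. Non-engagers can still attend. Section 4 asks all participants to come to the final visit, permits another study site for medical reasons, aims to allow up to 24 weeks, pays travel for everyone, and keeps high-risk participants for intention-to-treat. These steps should reduce missing walks.

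Finally, the bias need not be large or favorable. Using up the margin takes a 62.5 m shortfall in one arm only, about twice the 30 m minimally important difference (62.5 / 30 = 2.1). That is not a modest gap.

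All of this stands, and it limits the point. It does not say what happens when a walk is still missing, which the plan itself expects for 20%. An app-use trigger can naturally exist only in the arm that has the app, but that does not remove its conflict with section 7.

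**Conclusion.** The point holds as a gap between promise and method. Section 7 commits to including discontinued and non-engaging participants, but gives no means of including those without a 12-week 6MWT, up to 40 of 200. By default the noninferiority test would be complete-case, and the one-sided app-use rule in section 4 contradicts the commitment.

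The documents do not support saying that the result will be biased, or in which direction. The increases to about 10%, 15% and 32% (about 5%, 9% and 22% from a nominal 2.5%) rest on 20% missing in each arm, on assumed shortfalls of 30, 50 and 100 m in the intervention arm only, on SD 107 m among those observed, and on a true difference at the margin. With equal rates and equal shortfalls the bias is zero. Within that range the bias is comparable to the 12.5 m margin, and no planned analysis would reveal it.

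**What to change.** Before outcomes are compared by arm, amend section 7 as follows.

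1. Make the primary analysis cover all randomized participants, with multiple imputation of the 12-week 6MWT done separately by arm. Use age, sex, treatment modality, baseline survey scores and, where available, the pre-discharge 6MWT. That walk is mentioned only for hospital-enrolled patients, so the imputation model must not depend on it. Other prespecified methods that include all randomized participants could also serve.
2. Keep the observed-case regression, under that name, as supportive.
3. Add a tipping-point analysis that worsens only the imputed intervention-arm values until noninferiority is lost, and report the shortfall at which this happens.
4. State how death and inability to walk are handled. Setting them to 0 m answers a different question (a different estimand), so use it only as a sensitivity analysis.
5. Reconcile the lost-to-follow-up definition in section 4 with section 7, so that stopping the app does not by itself remove anyone from the 12-week measurement or the analysis.

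The cost is SAP wording, a little programming and possibly a slightly wider interval. The imputation uses data already planned for collection, and the 160 and 200 stay as they are.
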